6.3.2 Discontinuation from Study Participation

A subject in either the sipuleucel-T or control study arms will end study participation, including discontinuation of sipuleucel-T (sipuleucel-T arm only), biopsy and blood sample collection, for any of the following reasons:

- The subject withdraws consent or loses the ability to provide informed consent to participate in the study for any reason
- The subject is diagnosed with locally advanced or metastatic prostate cancer
- The subject dies or is lost to follow-up ([Section 6.5](#))

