6.3 Discontinuation from Study

A subject may discontinue participation in the trial at any time without prejudice. If a subject withdraws consent for any further study involvement, complete withdrawal of consent must be documented in the subject's medical record. The date and reason for withdrawal will be recorded in the subject's medical record and on the eCRF.

Whenever possible, every subject who withdraws consent and discontinues from the study will undergo an Early Withdrawal Visit within 30 days following discontinuation notice. Subjects are encouraged to have, as standard of care, a systematic prostate biopsy (≥ 10 cores) with or without MRI at the investigator's discretion prior to study withdrawal. The H&E and special-stained slides from this biopsy will be submitted for BICR determination of their ISUP Grade Group classification prior to study withdrawal. All AEs considered by the investigator to be related to sipuleucel-T that are ongoing at the time of discontinuation will be followed by the investigator until resolution, return to baseline, or a determination by the investigator that no further improvement is expected. The investigator should make every reasonable attempt to ensure that the subject is contacted (via telephone or during the Early Withdrawal Visit) to obtain the final status of any AEs and concomitant medications.

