6.7 Restricted Therapies During Sipuleucel-T Treatment Period

Certain therapies and procedures could confound the results of this study. Therefore, subjects who are randomized to the sipuleucel-T arm and receive any of the following, 30 days prior to the first infusion until 30 days after the last infusion, will discontinue sipuleucel-T treatment (Section 6.3.1):

- Any immunosuppressive therapy, including systemic steroids. Use of inhaled, intra-nasal, intra-articular, and topical steroids is allowed. Oral or IV steroids to prevent or treat IV contrast reactions are allowed
- Blood products
- GM-CSF or G-CSF
- Any vaccinations

Subjects that discontinue sipuleucel-T treatment and have received > 0 mL of sipuleucel-T will remain in the Active Phase and follow the schedule of events (Table 1).

6.8 Restricted Therapies from Randomization to End of Active Phase (Sipuleucel-T and Control Arms)

Certain therapies and procedures could confound the results of this study. Therefore, subjects who receive any of the following will go from Active Phase of the study to the Follow-up Phase of the study:

- Any local or systemic therapy or procedures for prostate cancer (e.g., ADT, radical prostatectomy, external beam radiation or brachytherapy)
- Any local or systemic therapy or procedure targeting the prostate (e.g., transurethral resection of the prostate (TURP) or 5-alpha reductase inhibitor)
- Major surgery at the discretion of the sponsor's Medical Monitor
- Any investigational product for prostate cancer or other condition (per sponsor's Medical Monitor approval)
- Any other therapy at the discretion of the sponsor's Medical Monitor

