- ^a All screening/baseline procedures must occur within 30 calendar days prior to randomization, with the exception of written informed consent and diagnostic biopsy
- ^b Randomization is the final event of Screening once eligibility of subject is confirmed by the PI.
- ^c Pre-study biopsy(ies) is (are) not a study procedure and the first diagnosed biopsy must have been performed ≤ 12 months of signing ICF. The biopsy (ies) H&E and special stained slides that were used for prostate cancer diagnosis must be submitted for BICR to determine subject eligibility.
- ^d Complete PE including vital signs done at the clinical site at Screening (genitourinary, skin, pulmonary, cardiovascular, neurological, gastrointestinal & musculoskeletal) and abbreviated PE per PI's discretion within 7 days prior to each leukapheresis and End of Active Phase Visit. Weight will be measured at each PE; height will be measured at Screening only.
- ^e The 26-week post-first-infusion visit and first 6-month visit post randomization may occur on the same visit day and only one set of immune samples need to be collected if the visits fall on the same day.
- ^f Survival status will not be obtained for subjects that are lost to follow up or withdrawn from the study.
- ^g PSA should be collected prior to DRE and biopsy procedures.
- ^h Any prostate cancer treatment (e.g., surgery, radiation, androgen deprivation therapy).
- ⁱ Patient reported outcomes/Quality of life questionnaire (IPSS, Max-PC, SF-12 and EPIC-CP) should be collected every 12 months (12-, 24-, and 36-month visits) prior to any procedures.
- ^j Biopsy 1 may take place between 12 months and 18 months post randomization. Biopsy 2 may take place between 33 months and 39 months post randomization.
- ^k Immune monitoring sample collection time points are calculated from the date of first infusion (note: not from randomization). Samples collected on infusion days (i.e., Weeks 0, 2, 4) will be drawn prior to starting the sipuleucel-T infusion. A single PAXGENE DNA sample is only collected at Week 0.
- ^l Blood draws for immune response analyses: 100mL total draw (90ml into NaHeparin Vacutainer for PBMC isolation and 10mL into no-anticoagulant vacutainer tubes for serum isolation).
- ^m Viral serology consists of hepatitis panel (HBsAg, HBsAb, HBcAb, HCV antibody(Ab), if Ab+ then HCV RNA)), HIV-1, HIV-2 antibody screen, and HTLV-1, HTLV-2 antibodies
- ⁿ End-of-Active Phase visit will take place within 30 days following Biopsy 2.

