9.1.4 Recording and Reporting Adverse Events

All AEs and SAEs in the sipuleucel-T arm and control arm will be collected from randomization through the subject’s last study visit. AEs and SAEs will be reported and recorded in the subject’s medical record and entered on their eCRF.

All AEs and SAEs reported in either the sipuleucel-T or control arms will be followed by the investigator until resolution, return to baseline, or the investigator determines that no further improvement is expected until study completion. The start and stop dates, description, seriousness, toxicity, relationship to study treatment, and outcome will be recorded.

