8.1.2.2 Time to the First Subsequent Prostate Cancer Treatment

The first prostate cancer treatment is the treatment with the earliest start date on the Systemic Prostate Cancer Therapy or Non-Systemic Prostate Cancer Therapy CRF. The time to first prostate cancer therapy (weeks) is defined as (earliest start date of all prostate cancer therapies – date of randomization + 1)/7. Censoring rules applied to time to prostate cancer therapy are:

- If start date for any treatment is missing, then censor event time at randomization date
- If no post-randomization assessment for prostate cancer treatments, then censor event time at randomization date
- If no subsequent prostate cancer treatment, then censor event time at the date of the last assessment for prostate cancer treatments

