12.7.2 Deaths and Serious Adverse Events

A summary and listing of deaths from all causes will be presented for all subjects randomized, overall and by study treatment arm. See [Section 12.7.1](#) for analyses of AEs that lead to death and SAEs.

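### Diagnosis of locally advanced or metastatic disease ends study participation, leaving no route for treatment, SAE or survival data after the last visit

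*Protocol*

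**What the plan says.** **Exit rule.** Protocol 6.3.2 lists the reasons for which a man in either arm "will end study participation, including discontinuation of sipuleucel-T (sipuleucel-T arm only), biopsy and blood sample collection". Beside withdrawal of consent, death and loss to follow-up stands "The subject is diagnosed with locally advanced or metastatic prostate cancer".

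**Rule for treated men.** Under Protocol 6.8, for prostate cancer therapy and certain other interventions, "subjects who receive any of the following will go from Active Phase of the study to the Follow-up Phase of the study". Protocol 5.1 has that phase assess survival, PROs, PSA, disease progression, prostate cancer therapies, AEs and SAEs every 6 months.

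**Data at and after exit.**
- Protocol 9.1.4 and 9.2.2 collect AEs and SAEs from randomization to the last study visit.
- The footnotes to Tables 1 and 2 state: "Survival status will not be obtained for subjects that are lost to follow up or withdrawn from the study".
- Protocol 6.3 says that, where possible, "every subject who withdraws consent and discontinues from the study will undergo an Early Withdrawal Visit within 30 days following discontinuation notice". SAP 6.1 applies that visit, again where possible, to anyone who discontinues before the end of the Active Phase.
- The Early Withdrawal column of Tables 1 and 2 (Protocol 8.1) includes AEs/SAEs, prostate cancer treatment, survival status, PSA and PROs. Protocol 6.3 also has related AEs that are ongoing at discontinuation followed up.

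**Analysis.**
- SAP 12.6.2.1 reports counts and proportions treated in the ITT and PP sets, plus Kaplan-Meier estimates of time to first treatment.
- SAP 8.1.2.2 states: "If no subsequent prostate cancer treatment, then censor event time at the date of the last assessment for prostate cancer treatments".
- SAP 12.7.2 states: "A summary and listing of deaths from all causes will be presented for all subjects randomized".
- SAP 8.1.1 counts a missing Biopsy 2 grade as failure in the primary analysis. The last-observation-carried-forward (LOCF) analysis in SAP 12.6.1.3 counts a man with a baseline grade and no recorded upgrade as a success.

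**The concern.** The other main reasons in 6.3.2 (withdrawn consent, death, loss to follow-up) make further data impossible or improper to collect. A diagnosis of spread does neither. The milder forms of progression are handled the other way: an upgraded man who stays on surveillance remains in the Active Phase (Protocol 8.11), and a man who starts therapy goes to Follow-up.

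The exit falls where treatment becomes likely. The background in Protocol 2.1.1 names upgrading and reclassification to cT3 or higher as the indicators for an immediate switch to active treatment, and the inclusion criteria require candidates for curative therapy should progression occur. Receipt of further therapy, and the reasons for it, is a secondary objective. At stake are that endpoint, the time-to-treatment curve, one sensitivity analysis of the primary endpoint, and safety and survival data on the gravest outcome in an open-label trial.

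**Working it through.** **1. The plan's own figure.** With 0.84 versus 0.70 upgrade-free, 300 versus 150 men and one-sided alpha 0.025, the unpooled standard error is √(0.70×0.30/150 + 0.84×0.16/300) = 0.0430. Power is Φ(0.14/0.0430 − 1.96) = 90.3%. A continuity-corrected calculation gives 90.2%, one-sided Fisher exact 90.3% and the pooled form 92.1%. The stated 90% reproduces, and nothing below changes it.

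**2. Path of a man diagnosed with spread, untreated at that point.** Consent has not been withdrawn.
- At exit: an Early Withdrawal visit, if held, records treatment, AEs/SAEs and survival to that date. By the protocol's wording he may not qualify for the visit; by the SAP's wording he does.
- After exit: no visit is scheduled, AE and SAE collection has ended, and survival is not obtained if he is classed as withdrawn.

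**3. The same man if treated first.** Protocol 6.8 sends him to Follow-up and his treatment is recorded. If spread is found at or after prostatectomy, 6.3.2 and 6.8 both apply and neither takes precedence.

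**4. Entry into each analysis, if first treated after exit.**

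| Analysis | Result |
|---|---|
| Primary (SAP 8.1.1) | Failure if Biopsy 2 grade is missing |
| LOCF sensitivity (SAP 12.6.1.3) | Success if no upgrade was graded |
| Proportion treated, ITT (SAP 9.1, 12.6.2.1) | In denominator, not in numerator |
| Time to first treatment (SAP 8.1.2.2) | Censored at last assessment; informative |
| Deaths, all randomized (SAP 12.7.2) | A death after exit may be missing |

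**5. How many men.** The documents give no rate for this trial. The only related figures are in Protocol 2.1.1: 25% to 45% of men had left surveillance after 5 to 15 years, and stage progression was 3% of the reasons. Reading the 3% as a share of leavers:
- 0.03 × 0.25 = 0.75%, and 0.0075 × 450 = 3.4 men
- 0.03 × 0.45 = 1.35%, and 0.0135 × 450 = 6.1 men

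**6. Effect on the proportion treated.** If a share *a* of an arm exits this way and a fraction *u* of them start first treatment after the last visit, that arm's proportion is understated by *a* × *u*. Taking *u* from 0.5 to 1 as an assumption, the understatement runs from 0.0075 × 0.5 = 0.4 points to 0.0135 × 1 = 1.35 points.

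**7. Effect on the difference between arms.** The shift is (*a* control − *a* sipuleucel-T) × *u*, which is zero when the rates are equal. As an outer bound with *u* = 1, six exits all in control give 6/150 = 4 points, and six all in sipuleucel-T give 6/300 = 2 points. More exits in control would hide a benefit on this endpoint.

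**The case against.** The strongest reply is that the gap is narrow. Data to the last visit are kept, the Early Withdrawal visit covers treatment, AEs/SAEs and survival, and related AEs ongoing at exit are followed. Protocol 9.2.3 also has deaths during the study reported. Most of this stands. A reader might infer that treatment, SAEs and survival are not collected at all for these men. The documents do not support that: only data after the last visit are lost. The death-reporting rule does not close that gap, because 9.2.2 limits SAE reporting to the period up to the subject's last study visit.

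A reader might also infer that these men count as untreated throughout. That fits only the ITT proportion, and only when no treatment was recorded before exit. The Kaplan-Meier analysis censors them. Nor is it certain that each man exits before treatment, since some would be diagnosed at or after surgery.

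On size, one might assume that 1% to 5% of 450 men exit, about 5 to 23 men. Nothing in the documents supports the upper end; the proxy points to the low end and covers a longer period than 36 months.

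Finally, SAP 12.6.2.1 treats subsequent treatment descriptively, although Protocol 10.5.2 names a Cochran-Mantel-Haenszel comparison. This limits the inferential damage but does not restore the data.

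**Conclusion.** The point holds for data after the last visit, and it should be fixed. Followed as written, the plan stops observing men at diagnosis of spread without their having withdrawn consent, and leaves the overlap between 6.3.2 and 6.8 unresolved. The ITT proportion treated is then undercounted, censoring in time to first treatment is informative, an LOCF success is possible for a man with spread, and the promised death summary may be incomplete.

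A reader might infer that the primary result is biased in favour of treatment. It is not: an exit without a Biopsy 2 grade is a failure in either arm.

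The likely size is about 3 to 6 of 450 men and roughly 0.4 to 1.35 points per arm, with little change in the absolute difference if exit rates are equal. This rests on the proxy, which comes from a different cohort with longer follow-up and counts stage progression only as a reason for leaving surveillance. It also rests on the assumed 50% to 100% first treated after the last visit. The case for acting lies in the gravity of these outcomes and the low cost of recording them, not in their number.

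**What to change.** Change data collection only.

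1. Keep the 6.3.2 bullet and its existing wording on sipuleucel-T, biopsies and blood samples. Deleting it would be a mistake: 6.3.1 does not name this diagnosis, so the bullet is the text that links it to stopping sipuleucel-T. Add that a man who exits for this reason enters the Follow-up Phase for the existing 6-monthly collection of survival, prostate cancer treatment, AEs/SAEs and PROs, unless he withdraws consent.
2. Reconcile 6.3.2 with 6.8, so that a man who meets both has one defined path.
3. Align the Early Withdrawal wording of Protocol 5.1 and 6.3 with SAP 6.1.
4. In the SAP, state how these men enter the proportion-treated and time-to-treatment analyses, and that they are not LOCF successes by default.

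The cost is a short protocol amendment, a few SAP sentences, and extra follow-up visits and SAE reports for a small number of men.

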6.4 Replacement of Subjects

Subjects who are randomized to the sipuleucel-T arm, but do not receive any sipuleucel-T (>0 mL) may be replaced.

6.5 Lost to Follow-up

If a subject fails to respond to requests for follow-up, the clinical trial site will send a certified letter, at a minimum, to the subject requesting contact with the clinic. All attempts to resume contact (including copies of written correspondence) will be included in the subject's medical record. Subjects who do not respond to requests for follow-up after all the above attempts to establish contact will be considered lost to follow-up.

6.6 Permitted Therapies

Subjects should receive full supportive care in accordance with standard practice at the clinical trial site.

Subjects who are receiving non-prostate cancer therapies (prescription or over-the-counter) at the time of randomization (that are not restricted ([Section 6.7](#))) should continue per the discretion of the prescribing physician.

6.7 Restricted Therapies During Sipuleucel-T Treatment Period

Certain therapies and procedures could confound the results of this study. Therefore, subjects who are randomized to the sipuleucel-T arm and receive any of the following, 30 days prior to the first infusion until 30 days after the last infusion, will discontinue sipuleucel-T treatment (Section 6.3.1):

- Any immunosuppressive therapy, including systemic steroids. Use of inhaled, intra-nasal, intra-articular, and topical steroids is allowed. Oral or IV steroids to prevent or treat IV contrast reactions are allowed
- Blood products
- GM-CSF or G-CSF
- Any vaccinations

Subjects that discontinue sipuleucel-T treatment and have received > 0 mL of sipuleucel-T will remain in the Active Phase and follow the schedule of events (Table 1).

6.8 Restricted Therapies from Randomization to End of Active Phase (Sipuleucel-T and Control Arms)

Certain therapies and procedures could confound the results of this study. Therefore, subjects who receive any of the following will go from Active Phase of the study to the Follow-up Phase of the study:

- Any local or systemic therapy or procedures for prostate cancer (e.g., ADT, radical prostatectomy, external beam radiation or brachytherapy)
- Any local or systemic therapy or procedure targeting the prostate (e.g., transurethral resection of the prostate (TURP) or 5-alpha reductase inhibitor)
- Major surgery at the discretion of the sponsor's Medical Monitor
- Any investigational product for prostate cancer or other condition (per sponsor's Medical Monitor approval)
- Any other therapy at the discretion of the sponsor's Medical Monitor

7.0 SIPULEUCEL-T TREATMENT

7.1 Overview

Dendreon will supply sipuleucel-T that must be stored, handled, prepared, administered, and labeled as specified by the current version of the sipuleucel-T Investigator's Brochure.

Accountability documentation must be maintained to ensure that sipuleucel-T is accurately administered. Such documentation will note request, shipment, receipt, storage, dispensation, administration, destruction, return, and use of required processes.

7.2 Sipuleucel-T Treatment

7.2.1 Leukapheresis and Infusion Scheduling

Once a subject has completed screening assessments and has been confirmed to be eligible and randomized to the sipuleucel-T arm, Dendreon will designate a leukapheresis center and the site will request a schedule for the subject's leukapheresis procedures to occur at approximately 2-week intervals. The date of each leukapheresis procedure will determine the date for the subsequent infusion of sipuleucel-T (approximately 3 days later).

The clinical trial site will receive confirmation of the leukapheresis and infusion dates and will schedule the subject's infusion appointments accordingly. If the subject is subsequently deemed ineligible for the study, the clinical trial site will be informed and the leukapheresis and infusion appointments will be canceled.

7.2.2 Pre-leukapheresis Assessments

Prior to each leukapheresis, subjects will undergo a pre-leukapheresis assessment to determine their suitability for the leukapheresis procedure. The pre-leukapheresis assessments including any requested tests by the apheresis center should be done within 7 days prior to each leukapheresis.

If a subject has any infection requiring parenteral antibiotic therapy or causing fever (temperature > 100.5°F or > 38.1°C) within 7 days prior to a leukapheresis appointment, the appointment should be rescheduled to occur after the fever resolves and the investigator believes the subject is healthy enough to undergo the procedure.

7.2.3 Subject Preparation for Leukapheresis

The subject should be instructed to eat calcium-rich foods in advance of the leukapheresis procedure. The subject should also be instructed to drink plenty of fluids a few days prior to the procedure to promote adequate venous access during leukapheresis, but to avoid drinking caffeinated beverages on the day of each leukapheresis procedure.

7.2.4 Leukapheresis

To manufacture of one dose of sipuleucel-T, the subject will undergo leukapheresis in order to collect PBMC. All PBMC collected from one leukapheresis procedure will be used to produce one dose of sipuleucel-T. Immediately after completion of the leukapheresis procedure, the PBMC are transported to a Dendreon immunotherapy manufacturing facility (IMF).

7.2.5 Sipuleucel-T Infusion

Each sipuleucel-T product is released by Dendreon for infusion approximately 3 days after the leukapheresis procedure. The clinical trial site will provide all supplies required for infusion.

Sipuleucel-T must be administered under the supervision of an investigator experienced in the medical treatment of prostate cancer and in an environment where resuscitation equipment is available.

7.2.6 Sipuleucel-T Product Failures and Leukapheresis Rescheduling

A subject may be scheduled for a repeat leukapheresis procedure if the subject's leukapheresis procedure fails, sipuleucel-T does not meet quality release specifications, sipuleucel-T infusion is not started prior to its expiration, or for various other reasons. Rescheduling will depend upon the capacities of the leukapheresis center and the Dendreon IMF, and ≥ 2 weeks should elapse between one leukapheresis procedure and the next (1-week interval may be approved at the discretion of the Medical Monitor).

If a subject's subsequent leukapheresis procedure is delayed or rescheduled for any reason, all protocol-specified pre-leukapheresis assessment conditions apply.

In rare instances, it may be determined for a given subject that it is not possible to manufacture sipuleucel-T that meets manufacturing release specifications ([Section 6.3.1](#)).

7.3 Timing of Dose for Each Subject

Subjects will receive 3 infusions of sipuleucel-T at approximately 2 week intervals. Each dose of sipuleucel-T contains a minimum of 50 million autologous CD54+ cells activated with recombinant fusion protein composed PAP linked to GM-CSF (PA2024).

